11.3 Analysis Plan for Endpoints

11.3.1 Primary Endpoints

The primary endpoint of CR will be calculated, and a 90% Clopper-Pearson confidence interval will be estimated via exact binomial proportions.

11.3.2 Secondary Endpoints

With adequate follow-up time, secondary endpoints of progression-free survival (PFS), overall survival (OS), and time to next treatment will be assessed by Kaplan-Meier survival analysis and 90% confidence intervals will be calculated using Greenwood's formula. PFS will be defined as the time from first treatment day until objective or symptomatic progression or death. OS will be defined as the time from first treatment day until death. TTNT will be defined as time from end of primary treatment to institution of next therapy.

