1.2 Secondary Objectives

- Safety and tolerability of the ALR combination
- Best overall response rate
- Complete response rate
- Progression free survival (time frame up to 2 years)
- Overall survival (time frame up to 2 years)
- Safety and feasibility of the ALO cohort

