5.5 Duration of Therapy

The study includes an induction phase consisting of 12 cycles of ALR or ALO. Responding subjects will be eligible to enter a maintenance phase. Subjects will continue maintenance ALR or ALO until disease progression, development of unacceptable toxicity, or voluntary withdrawal. Acalabrutinib and lenalidomide can be discontinued after 24 cycles of treatment (12 cycles of induction and 12 cycles of maintenance) for subjects achieving MRD-negative CR during maintenance phase. Subjects have the option to complete study after a total of 3 years of study treatment at the discretion of the treating physician. Subjects can be retreated with acalabrutinib and lenalidomide at time of disease progression.

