5.6 Duration of Follow Up

The Follow-up Period for each subject begins upon study treatment discontinuation. A treatment discontinuation safety visit occurs within 28 days of treatment discontinuation. Subjects will be followed for subsequent anti-lymphoma therapies and survival every 6 months according to the schedules described in Tables 1 and 2.

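### Time to next treatment starts at an undefined end of primary treatment; if that means study treatment discontinuation, patients still on therapy have no time zero and those treated to progression start at failure

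*Combined protocol and SAP*

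**What the plan says.** The Endpoints entry of the Protocol Summary names time to next treatment (TTNT) as a secondary endpoint of the ALR combination. Section 11.3.2 gives its whole specification: "time to next treatment will be assessed by Kaplan-Meier survival analysis", with 90% intervals by Greenwood's formula, and "TTNT will be defined as time from end of primary treatment to institution of next therapy". The same section measures its companion endpoints from the start of therapy: "PFS will be defined as the time from first treatment day until objective or symptomatic progression or death", and OS likewise from the first treatment day.

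Therapy has no fixed length. After 12 induction cycles, section 5.5 says: "Subjects will continue maintenance ALR or ALO until disease progression, development of unacceptable toxicity, or voluntary withdrawal". It adds: "Subjects have the option to complete study after a total of 3 years of study treatment at the discretion of the treating physician". Sections 5.1 and 5.5 allow acalabrutinib and lenalidomide to stop after 24 cycles in patients with MRD-negative CR; section 5.1 adds that the antibody continues. Both sections allow the two oral drugs to be given again at progression.

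On follow-up, section 5.6 says: "The Follow-up Period for each subject begins upon study treatment discontinuation", and "Subjects will be followed for subsequent anti-lymphoma therapies and survival every 6 months".

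**The concern.** A start at the end of treatment is workable when treatment has a fixed length. Here patients leave therapy at different times and for different reasons, and the plan does not say which ending counts. Two analysts could draw different curves from the same data.

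The reading with the most support elsewhere in the text is discontinuation of all study treatment, because section 5.6 begins follow-up for later therapies there. On that reading, entry to the analysis depends on something that happens after baseline. A patient who is still responding on therapy is absent from the curve. A patient treated to progression enters at the moment of failure. A patient who stops in remission, for toxicity or at planned completion, may contribute a long interval that reflects the reason for stopping and not better disease control.

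At stake is whether a named ALR endpoint can be interpreted.

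**Working it through.** **1. Candidate start points**

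| Reading of the start point | Support in the text | Consequence |
|---|---|---|
| End of induction | 12 cycles, sections 5.1 and 5.5 | Patients who leave earlier, for example those removed under section 6.8 for no PR after 3 or 6 cycles, have no stated start date |
| End of the oral drugs | Optional after 24 cycles, sections 5.1 and 5.5 | The planned stop is open only to patients in MRD-negative CR, and antibody treatment goes on past time zero |
| End of all study treatment | Follow-up begins there, section 5.6 | No time zero while on therapy; start at failure for those treated to progression |

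No passage selects one of these.

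**2. How many would lack a time zero if all study treatment is meant**

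The plan gives no figure for TTNT, so there is none to reproduce. The following is an illustration of scale.

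- From the documents: 4-year PFS of 70% for lenalidomide plus rituximab (section 2.1) and 28 ALR patients (section 11.2).
- Assumed: ALR has the same PFS, hazards are constant, every PFS event is a progression, a fraction x of 0 to 0.25 stops for toxicity by 24 months, and there are no other withdrawals.
- Monthly hazards: progression −ln(0.70)/48 = 0.00743; toxicity stop −ln(1 − x)/24, which is 0.01199 at x = 0.25.
- Share still on treatment at month t: 0.70^(t/48) × (1 − x)^(t/24).

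| Months from first dose | x = 0 | x = 0.25 |
|---|---|---|
| 24 | 0.837 | 0.628 |
| 36 | 0.765 | 0.497 |
| 48, nobody completes at 3 years | 0.700 | 0.394 |
| 48, half complete at 3 years | 0.350 | 0.197 |
| 48, all complete at 3 years | 0 | 0 |

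Twenty-four months is the horizon in section 1.2: "Progression free survival (time frame up to 2 years", and the same for OS. At that point 28 × 0.837 = 23.4 and 28 × 0.628 = 17.6 patients would have no time zero, leaving 4.6 to 10.4 on the curve. Among those who have stopped, the share who stopped at progression is 100% at x = 0, and 0.00743/(0.00743 + 0.01199) = 38% at x = 0.25.

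A second set of assumptions agrees. With the doublet's 2-year PFS of 85% (section 2.1) and other stops at 0 to 10% per year, 28 × 0.85 = 23.8 and 28 × 0.85 × 0.90² = 19.3 patients are still on therapy at two years.

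**3. How many leave early if the end of induction is meant**

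Twelve 28-day cycles are 336 days, or 11.04 months. Under the assumptions of step 2, the share leaving before then is 1 − exp(−0.00743 × 11.04) = 0.079 at x = 0 and 1 − exp(−0.01942 × 11.04) = 0.193 at x = 0.25, about 2 to 5 of 28.

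**4. Rules the section does not give**

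The event is the start of next therapy alone, whereas PFS in the same section includes death. Death is therefore not a TTNT event as written, but the plan does not say whether it is censored or treated as a competing event. Nor does it say whether giving acalabrutinib and lenalidomide again at progression counts as next therapy. Choosing a start point settles neither question.

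**The case against.** The strongest reply is that the fault is an undefined term and not a wrong start point. An interval after stopping is a coherent quantity, and section 2.3 states an interest in time off the oral drugs. On the induction reading, 81 to 92% reach the end of cycle 12 under the assumptions above, so the two main harms largely disappear. TTNT also has no hypothesis or decision rule and is absent from the secondary objectives in section 1.2. All of this limits the weight of the point. It does not remove it, since the plan does not choose a reading and the one that section 5.6 favours gives a misleading curve.

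Three stronger inferences are tempting, and the documents do not support them.

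- *The curve would always rest on a minority of patients.* In the illustration this holds at 24 months. By 48 months 30 to 61% have stopped if nobody completes at 3 years, and all have stopped if everyone does. Section 11.3.2 sets no data cut beyond adequate follow-up.
- *Worse tolerability would improve TTNT by a calculable amount.* The direction is possible. Its size depends on how soon patients who stop for toxicity or progression receive another therapy, and the documents give no such figures. If all toxicity stops went straight to new therapy, there would be no such gain.
- *Patients who leave induction early can never have a time zero.* The text refers to an end and not to completion of 12 cycles, so their leaving date could serve. The plan simply does not say so.

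**Conclusion.** The concern holds in a limited form. The start point of TTNT is undefined. If it is discontinuation of all study treatment, entry to the curve depends on leaving therapy, and the curve cannot be read as a description of how ALR delays the next treatment. In the illustration about 63 to 84% of patients lack a time zero at 24 months and 50 to 77% at 36 months. At 48 months the range is 0 to 70%, depending mostly on use of the 3-year option. These figures rest on the doublet's PFS, constant hazards and an assumed 0 to 25% of toxicity stops; they show scale and are not forecasts. If the end of induction is meant, the gap is smaller: early leavers have no stated start date.

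The definition should be corrected before analysis. The damage is confined to one descriptive secondary endpoint. The primary endpoint, PFS, OS and the stopping rules are unaffected.

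**What to change.** In section 11.3.2, define TTNT as the time from first treatment day to the start of the next anti-lymphoma therapy, in all treated ALR patients, with patients alive and without next therapy censored at last contact. All treated ALR patients then enter on day 1, as for PFS and OS.

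Add two rules:

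- How death before next therapy is handled. Counting it as an event fits the Kaplan-Meier method already named. Treating it as a competing event calls for a cumulative incidence curve instead.
- Whether add-back of acalabrutinib and lenalidomide at progression counts as next therapy. If it does, its date comes from the treatment record, since it may occur while antibody maintenance continues.

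If the interval after stopping is of interest, report it as a separate description, with its start defined for each way of leaving therapy, its denominator and the reasons for stopping.

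The cost is a few sentences and no new data. Section 5.6 already follows later therapies and survival, section 10.1 captures treatment data, and section 5.4.2 prohibits other anti-cancer therapy during the treatment period. The downside is overlap with PFS, because many patients are treated to progression.

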11.3.3 Correlative Endpoints

The frequency of subjects experiencing adverse event will be tabulated. Paired t-test will be performed to assess the differences between baseline and the end of treatment for numerical variables, such as gene expression, immunophenotypic changes, cfDNA, etc. All p-values will be two-sided with statistical significance evaluated at the 0.1 alpha level. Ninety percent confidence intervals will be calculated to assess the precision of the obtained estimates. All analyses will be performed in SAS Version 9.4 (SAS Institute, Inc., Cary, NC).

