- Use of any other experimental drug or therapy within 28 days of baseline
- Patient at high risk for deep vein thrombosis not willing to take DVT prophylaxis
- Any significant medical condition, laboratory abnormality, or psychiatric illness that would prevent the subject from participating in the study

- Known prior exposure to BTK inhibitor

Accrual Period:

07/2019 – 07/2022

Study Design:

This is a phase 2 study to evaluate the preliminary evidence of efficacy and safety of the combination of acalabrutinib, lenalidomide and rituximab (ALR), as well as acalabrutinib, lenalidomide and obinutuzumab (ALO), in previously untreated mantle cell lymphoma.

Study Duration:

Study includes an induction phase consisting of 12 cycles of ALR or ALO. Responding subjects will be eligible to enter a maintenance phase. Subjects will continue maintenance ALR or ALO, until disease progression, development of unacceptable toxicity, or voluntary withdrawal. Acalabrutinib and lenalidomide can be discontinued after 24 cycles of treatment (12 cycles of induction and 12 cycles of maintenance) for subjects achieving MRD-negative CR during maintenance phase. Subjects can be retreated with acalabrutinib and lenalidomide at time of disease progression.

Study Agent/ Intervention Description:

Cohort A: ALR in MCL, phase 2 study

- **Induction** (cycles 1 - 12)
 - 12 cycles, 1 cycle = 28 days
 - Acalabrutinib 100 mg BID continuous
 - Lenalidomide on days 1-21 (15 mg for cycle 1, then escalate as tolerated to 20 mg)
 - Rituximab 375 mg/m² on days 1, 8, 15, 21 of cycle 1 then day 1 of cycle 4, 6, 8, 10, 12
- **Maintenance** (cycle 13 – progression of disease or unacceptable toxicity)
 - Ongoing, 1 cycle = 28 days
 - Acalabrutinib 100 mg BID continuous
 - Lenalidomide 15 mg on days 1-21
 - Rituximab 375 mg/m² on day 1 of all even numbered cycles; e.g., 14, 16, 18, etc.

Cohort B: ALO in MCL, feasibility cohort

- **Induction** (cycles 1 - 12)
 - 12 cycles, 1 cycle = 28 days
 - Acalabrutinib 100 mg BID continuous
 - Lenalidomide on days 1-21 (15 mg for cycle 1, then escalate as tolerated to 20 mg)
 - Obinutuzumab on days 1, 8, 15 of cycle 1, day 1 of cycles 2-6, then every 2 cycles
- **Maintenance** (cycle 13 – progression of disease or unacceptable toxicity)

- Ongoing, 1 cycle = 28 days
- Acalabrutinib 100 mg BID continuous
- Lenalidomide 15 mg on days 1-21
- Obinutuzumab on day 1 of all even numbered cycles; e.g., 14, 16, 18, etc.

Primary Objective:

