5.2.3 Treatment Discontinuation

At treatment discontinuation, subjects will undergo off study evaluations within 28 days of last dose.

- Physical examination with vital signs and performance status
- AE assessment
- CBC with differential
- Serum chemistries to include TFT, CMP, LDH, phosphate and uric acid
- Concomitant medications
- HBV viral DNA in HBcAb positive, asymptomatic carrier
- Correlative blood samples
- Pregnancy test (for females of childbearing potential)
- CT scan (or MRI) of neck/chest/abdomen/pelvis (and other areas if indicated to evaluate sites of disease involvement); PET scan at discretion of investigator
- FACT-Lym quality-of-life questionnaires
- Telemedicine/virtual visits will be allowed where physical exam and vital signs may not be collected.
- Follow-up contact every 6 months until death

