8.1.3 Circulating immune cells

Whole blood in 10mL purple-top tube will be collected at baseline, weekly for cycle 1, then on C2D1, C4D1, C6D1, and time of progression, and subject to real-time flow cytometric analysis of peripheral blood mononuclear cells (PBMCs) and TILs, including T-cell subsets, NK cells, and MDSC.

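### The correlative tests compare baseline with an undefined end of treatment, which does not match the specimen plan and, read as discontinuation, selects patients by outcome until the 3-year option opens

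*Combined protocol and SAP*

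**What the plan says.** Section 11.3.3 plans a single contrast for the numerical correlatives: "Paired t-test will be performed to assess the differences between baseline and the end of treatment for numerical variables". The examples it gives are cfDNA, immunophenotype and gene expression. On error control it adds: "All p-values will be two-sided with statistical significance evaluated at the 0.1 alpha level". It gives no definition of end of treatment, no scale or transformation, no rank-based alternative and no rule for undetectable results.

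Treatment has no fixed end. Section 5.5 says: "Subjects will continue maintenance ALR or ALO until disease progression, development of unacceptable toxicity, or voluntary withdrawal", and the Study Duration entry in the Protocol Summary agrees. Section 5.5 also allows a planned exit without failure: "Subjects have the option to complete study after a total of 3 years of study treatment at the discretion of the treating physician".

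The sampling text differs from place to place:

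- Section 5.2.3: "At treatment discontinuation, subjects will undergo off study evaluations within 28 days of last dose". Correlative blood is on that visit's list, with no assay named.
- Section 8.1.2: cfDNA at baseline and the MRD time points only. Cytokines follow the cycle 1 to C6D1 schedule, then the MRD frequency, then progression.
- Section 8.1.3: immune cells at baseline, weekly in cycle 1, then "C2D1, C4D1, C6D1, and time of progression".
- Sections 5.2.2.1 and 5.2.2.3, and footnote 11 of Table 1: correlative blood continues well past cycle 6 (cycles 7, 13, 17, 21, 25 and later, or at the MRD frequency).

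The exploratory objectives in 1.3 ask for change in response to treatment and, for cfDNA, for kinetics.

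**The concern.** In a trial that treats until progression, a discontinuation sample becomes available because of what happened to the patient. Someone still in remission on therapy has none, so drops out of the paired test. Those who remain were sampled at very different times, many of them at relapse. The contrast then mixes the effect of the regimen with the state of the marker at failure. Section 1.3 keeps these apart: its immune-metabolic objective lists post-ALR and progression as separate occasions.

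The second issue is scale. Where cfDNA, cytokine or cell-count values are strongly right-skewed, a t-test on recorded values is driven by a few patients. Leaving the scale and the treatment of undetectable values open also leaves those choices until after the data are seen.

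At stake is the interpretability and sensitivity of the exploratory biomarker results. No primary or secondary conclusion depends on them.

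**Working it through.** **1. Number of pairs.** Section 11.3.3 gives no sample size for the correlatives, so the ALR figure in 11.2 serves as reference. An exact binomial test of 60% against 80% at one-sided 0.10 with n=24 and success at 18 or more responders has alpha 0.0960 and power 0.8111. The plan's 24 is reproduced.

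**2. What end of treatment could mean.** Three readings are possible: the end of 12-cycle induction; stopping the oral drugs after 24 cycles while the antibody continues (5.1); or final discontinuation (5.2.3). The third is the ordinary one, and footnotes 7 and 8 of Table 1 use the term for an assessment after the on-treatment schedule. The text does not settle it.

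**3. Who supplies a discontinuation sample.** Inputs: 28 ALR patients (11.2); doublet PFS of 85% at 2 years and 70% at 4 years (2.1), assumed to apply here; constant hazard between those points.

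- 12 cycles = 336 days = 0.92 years: PFS = 0.85^(0.92/2) = 0.928; progressed or died = 28 × 0.072 = 2.0.
- 2 years: 28 × 0.15 = 4.2.
- 3 years: PFS = 0.85 × √(0.70/0.85) = 0.771; 28 × 0.229 = 6.4.

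Before 3 years no planned exit without failure exists, so every discontinuation sample comes from a patient who progressed or stopped early. PFS and OS have a 2-year time frame (1.2), so an analysis on that horizon falls in this period.

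After 3 years, assume 0-30% of the non-progressors stopped early for other reasons:

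- Early stoppers: 6.4 to 6.4 + 0.30 × 21.6 = 12.9.
- Share if all the others take the option: 6.4/28 = 23% to 12.9/28 = 46%.
- Early stoppers are the majority only if uptake is below 6.4/21.6 = 30% (no other stops) or 12.9/15.1 = 85% (30% other stops).

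**4. Effect of the mix (illustration; the marker values are assumed).** Let a marker fall to 0.20 of baseline on treatment and return to baseline at progression. With 6 progressors among 8 samples, the geometric mean ratio is exp[(6 ln 1 + 2 ln 0.2)/8] = 0.67. With a 23% progressor share it is 0.2^0.77 = 0.29. The on-treatment value is 0.20.

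**5. Scale.** The documents give no variances, so log-SD is varied. Paired log-normal values, correlation 0.5, true halving, two-sided 0.10, power by simulation:

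| n | log-SD | raw t | log t | signed-rank |
|---|---|---|---|---|
| 24 | 0.5 | 1.00 | 1.00 | 1.00 |
| 24 | 1.0 | 0.80 | 0.95 | 0.91 |
| 24 | 1.5 | 0.39 | 0.71 | 0.60 |
| 10 | 1.0 | 0.46 | 0.65 | 0.54 |
| 10 | 1.5 | 0.19 | 0.39 | 0.31 |
| 6 | 1.5 | 0.11 | 0.26 | 0.23 |

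Hand check of the log column: with correlation 0.5 the SD of the log difference equals the log-SD, so at n=24 and log-SD 1.5 the noncentrality is 0.693 × √24 / 1.5 = 2.26. Against a critical value of 1.71 this gives power of about 0.71.

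At log-SD 0.5 and n=24 all three tests are at the ceiling. With no true change, the raw t-test rejects in 0.03-0.10 of samples over n = 6, 10, 24 and log-SD 0.5-2.0, so it is conservative or on target.

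**6. Contrast against specimens.** For cfDNA, 8.1.2 names no end-of-treatment draw. For immune cells, 8.1.3 names only a progression draw after C6D1. Section 5.2.3 lists unspecified correlative blood for everyone who stops. These passages cannot all describe the same specimen plan.

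**The case against.** The strongest reply is that 11.3.3 never says end of all therapy. The primary endpoint is read after 12 cycles, and 11.3.2 starts time to next treatment at the end of primary treatment. If end of induction was meant, selection on progression largely disappears. That is fair, and it is why the defect is an undefined time point.

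A reader might infer that end-of-treatment samples will come mainly from failures. The documents do not support that for a late analysis: 5.5 opens a non-failure exit at 3 years, and 5.2.3 schedules blood for everyone who discontinues. Nor does the mechanism describe cfDNA under 8.1.2, where the fault is that no such draw is named.

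A reader might also infer that the plan prescribes a raw-scale test. It names no scale. Nor does the choice of test create false positives: type I error is not inflated. The loss of power rests on assumed log-SDs and vanishes at n=24 under mild skew. The mixing illustration dilutes a fall; it does not reverse it. A reversed sign would need the marker to exceed baseline at progression, which nothing in the documents shows.

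Finally, a fixed late time point has selection of its own, since 6.8 removes patients without at least PR after 3 or 6 cycles. This stands and is dealt with in the fix.

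**Conclusion.** The concern holds in a limited form. The stated contrast has an undefined second time point and is not matched by 8.1.2 and 8.1.3, which themselves disagree with 5.2.2, 5.2.3 and Table 1 footnote 11. On the ordinary reading, the pairs are selected entirely on outcome in any analysis before 3 years. After that the selection is partial and depends on uptake; the share figures rest on doublet PFS carrying over and on assumed rates of other early stops. The missing scale and undetectable-value rule matter in proportion to skew: nothing at log-SD 0.5 with 24 pairs, about 0.15 of power at 1.0 and about 0.32 at 1.5, all under assumed correlation 0.5 and a true halving. This should be corrected because scheduled samples give a better contrast, but it is confined to exploratory endpoints.

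**What to change.** Revise 11.3.3 as follows:

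- **Main contrast.** Compare baseline with a fixed on-treatment sample already scheduled: after cycle 12 for cfDNA and cytokines; C6D1 for immune cells, or a later draw once 8.1.3 is reconciled with 5.2.2 and 5.2.3.
- **Earlier contrast.** The cycle-12 contrast covers only patients still on study, so state this and also report an earlier fixed point, such as after cycle 6.
- **Scale.** Analyse log values by paired t-test with a pre-specified rule for undetectable results, or name in advance the markers to be tested by Wilcoxon signed-rank. Do not choose the test after seeing zeros.
- **Late samples.** Report progression and discontinuation samples separately, with numbers and sampling times.
- **Consistency.** Define end of treatment wherever it is kept, and align 5.2.2, 5.2.3, 8.1.2, 8.1.3 and Table 1 footnote 11 on which assays are drawn when.

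The cost is wording and a little extra analysis. No new samples are needed.
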